#### **4.4 Concomitant Medication and Treatment**

All concomitant medications and blood products administered to patients after the first dose of study drug, until 60 days after the last dose of study drug must be recorded on the case report form (CRF).

Permitted medication and therapies:

- Patients may receive non-myelosuppressive palliative radiation therapy if required. Concomitant radiation therapy with erlotinib treatment is allowed.
- Patients will receive full supportive care throughout the study, including transfusion of blood products, treatment with antibiotics, anti-emetics, anti-diarrheals, and analgesics as appropriate.
- Patients exhibiting dry eyes should be advised to use an ocular lubricant.

Not permitted:

- Administration of any other anti-cancer therapy (cytotoxic or biological/immunotherapy) is not permitted until after disease progression has been documented.
- Patients who have received study drug should not receive any other investigational drugs until after the post-treatment assessment (at least 60 days after the final dose of study drug).

Caution should be exercised when erlotinib is co-administered with CYP3A4 inhibitors and inducers. As grapefruit juice has the potential to inhibit CYP3A4 activity, patients should not eat grapefruit or drink grapefruit juice during the study.

#### **4.5 Criteria for Premature Withdrawal**

Patients have the right to withdraw from the study at any time for any reason.

In the case that the patient decides to prematurely discontinue study treatment (“refuses treatment”), he/she should be asked if he/she can still be contacted for further information. The outcome of that discussion should be documented in both the medical records and in the CRF. If lost to follow-up, the investigator should contact the patient or a responsible relative by telephone followed by registered mail or through a personal visit to establish as completely as possible the reason for the withdrawal. A complete final evaluation at the time of the patient’s withdrawal should be made with an explanation of why the patient is withdrawing from the study.

When applicable, patients should be informed of circumstances under which their participation may be discontinued by the investigator without the patient’s consent. The investigator may withdraw patients from the study in the event of intercurrent illness, adverse events, treatment failure after a prescribed procedure, lack of compliance with the study and/or study procedures (e.g., dosing instructions, study visits), cure or any reason where it is felt by the investigator that it is in the best interest of the patient to be withdrawn from the study. Any administrative or other reasons for withdrawal must be documented and explained to the patient.

If the reason for removal of a patient from the study is an adverse event, the principal specific event will be recorded on the CRF. The patient should be followed until the adverse event has resolved, if possible.

## **4.6 Replacement Policy (Ensuring Adequate Numbers of Evaluable Patients)**

### **4.6.1 For Patients**

Patients enrolled into the study will not be replaced.

### **4.6.2 For Centers**

A center may be replaced for the following administrative reasons:

- Excessively slow recruitment.
- Poor protocol adherence.

## **5. SCHEDULE OF ASSESSMENTS AND PROCEDURES**

The complete schedule of assessments is tabled in the synopsis of protocol (see Schedule of Assessments, page 8).

### **5.1 Screening Examination and Eligibility Screening Form**

The screening visit must occur no more than 7 days prior to the start of therapy. Information according to the Schedule of study assessments will be provided.

All patients must provide written informed consent before any study-specific assessments or procedures are performed.

#### **Diagnostic Phase**

Patients must meet all inclusion criteria and no exclusion criteria to be eligible for enrollment in the study.

After signing an Informed Consent Form (ICF) the patient's demographic data will be recorded in the Case Report Form (CRF) and the mandatory tumour sample will be taken in order to assess EGFR status. If a biopsy sample has already been taken prior to entry into the study, **there is no need** to re-take a new biopsy specimen for the purposes of the study. Tumour samples will be sent to laboratory for determination of EGFR mutation status. EGFR mutation analysis will be performed at [REDACTED] [REDACTED] for oncology and radiology of Serbia or at Private Laboratory [REDACTED].

#### **Treatment Phase**

The screening visit must occur no more than 7 days prior to the start of therapy. The following information will be recorded for all patients.

- Review of medical history
  - A physical examination including measurement of weight
  - Vital signs including ECG
  - Assessment of ECOG performance status
- Concomitant medications
- Tumour assessment

- Pregnancy test negativity (in women of childbearing potential). Patients who are amenorrhoeic for at least 12 months are not considered of childbearing potential. This must be performed within 3 days prior to starting therapy.

Samples will be collected for:

- Haematology
- Biochemistry

Patients will also be provided with the quality of life questionnaire (EQ5D) for completion at the screening visit.

## **5.2 Procedures for Enrollment of Eligible Patients**

After signing an Informed Consent Form (ICF) the patient's demographic data will be recorded in the Case Report Form (CRF) and the mandatory tumor sample will be taken in order to assess EGFR status.

## **5.3 Clinical Assessments and Procedures**

Clinical and safety assessments will be performed at Screening and Baseline and on Day 1 of every 6th week until PD, death, or unacceptable toxicity, as indicated in the Schedule of Assessments.

### **5.3.1 Tumor Response Criteria**

Tumor response will be evaluated according to RECIST criteria (Eisenhauer et al., 2009) (see Appendix 1).

#### **Methods of measurement**

The same method of tumor measurement and assessment must be used to characterize each lesion throughout the study.

#### **Scheduling of tumor assessments**

In this study, assessment of tumor progression during treatment with erlotinib will be performed every 6th week during the study visits and on the End of Study visit (as given in the Schedule of Assessments). Baseline total tumor burden must be assessed within a maximum of 2 weeks before first dose of study drug treatment. Post-baseline assessments are to be performed within +/- 1 week for the 6 weekly assessments. If there is suspicion of disease progression based on clinical or laboratory findings, a tumor assessment should be performed as soon as possible, before the next scheduled evaluation.

If a patient inadvertently misses a prescribed tumor evaluation or a technical error prevents the evaluation, the patient may continue treatment until the next scheduled assessment, unless signs of clinical progression are present.

Tumor response should be confirmed at a minimum of 4 weeks after initial response was noted, or at the next scheduled tumor assessment if it will occur more than 4 weeks after the response was first noted.

For the confirmation of Stable Disease (SD), follow-up measurements must have met the SD criteria at least once after study entry at a minimum interval of 6 weeks.

The diagnosis of disease progression will be made by objective criteria (RECIST criteria) on the target lesion(s), or by documenting, with CT/MRI scans or X-Rays, the presence of newly occurring lesion(s) arising outside the scanned areas of the target lesions.

### **5.3.2 Response Status at Each Visit**

All patients will have their response classified at each visit according to the RECIST criteria (see Appendix 1).

### **5.3.3 ECOG Performance Status**

Performance status will be measured using the ECOG performance scale (see Appendix 2), at screening, baseline and at each study visit on Day 1 of every 6th week of treatment period, and on the final visit at End of Study. It is recommended that a patient's performance status is assessed by the same person throughout the study.

### **5.3.4 Clinical Safety Assessments**

The NCI CTC-AE version 4.0 will be used to evaluate the clinical safety parameters of the study drug. Patients will be assessed for adverse events at each clinical visit from screening onwards and as necessary throughout the study.

Safety assessments will consist of monitoring and recording all AEs and serious adverse events (SAEs); regular monitoring of hematology, biochemical analyses, and urine test results, regular measurement of vital signs, and physical examinations. Twelve lead ECG recordings will be performed as part of the screening (baseline) assessments and at end of study. Additional electrocardiogram (ECG) monitoring will be performed if clinically indicated throughout the study.

## **5.4 Laboratory Assessments**

Normal ranges for the study laboratory parameters must be supplied to Roche before the study starts.

### **5.4.1 Efficacy Laboratory Assessments**

Laboratory parameters will not be considered for the purpose of efficacy assessment.

### **5.4.2 Safety Laboratory Assessments**

All safety laboratory assessments will be performed at local laboratories.

The safety laboratory assessments will be completed according to the Schedule of Assessments.

## **5.5. Quality of Life Assessments**

Quality of life will be measured using the FACT-L method. This is a validated measure of quality of life.

FACT-L Quality of Life questionnaires will be administered to patients prior to therapy, at each visit and at the final study visit, 4 weeks after patients progressed. See Appendix 5

## **6. INVESTIGATIONAL MEDICINAL PRODUCT (IMP)**

### **6.1 Dose and Schedule of IMP**

Erlotinib will be administered as a single daily oral dose of 150 mg. No dose escalation of erlotinib is permitted. Protocol treatment will begin within 24 hours after receiving positive activating EGFR mutation test result (exon 19 deletion or exon 21 substitution L858R) and will continue until disease progression, death or unacceptable toxicity.

#### **6.1.1 Dose Modifications, Interruptions and Delays**

Reduction/interruption of dosing for adverse events may take place at any time during the study.

Diarrhea and skin rash are the major side effects associated with erlotinib. Other known side effects include dry skin, fatigue, pruritus, nausea, vomiting, anorexia, abdominal pain, gastrointestinal perforation, dry mouth, dry eye, and headache. Dose reductions can be made according to the system exhibiting the greatest degree of toxicity. All toxicities will be graded according to the NCI CTC-AE version 4.0.

Upon the onset of an AE deemed by the investigator to be related to the study drug, treatment will be interrupted until AE resolution and then restarted at reduced dose of erlotinib. Once a patient has a dose reduction for toxicity, the dose will not be re-escalated except in the case of erlotinib related rash.

The dose of erlotinib will be decreased in 50 mg steps according to the schedule displayed in Table 1.

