**Table 1 Dose Level Reductions**

Starting Dose	First reduction	Second reduction
150 mg/day	100 mg/day	50 mg/day

The following guidelines in Table 2 outlines dose adjustments according to the most common toxic effects. In the event of a rash, dose can be re-escalated when rash is  $\leq$  grade 2. Should a patient experience more than one toxic effect, the dose should be reduced.

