**Table 2 Guidelines for management of erlotinib-related toxic effects:**

Toxicity	Grade	Guideline for management	Dose modification of erlotinib*
Keratitis	2	Interrupt the treatment. Ophthalmologic assessment.	Hold until recovery, and then restart at reduced dose. Continue regular ophthalmological assessments while

			on treatment.
	$\geq 3$	Discontinue treatment and seek ophthalmological advice	
Diarrhea	1	No intervention	None
	2	Loperamide (4 mg at first onset, followed by 2 mg every 2-4 hours until diarrhea-free for 12 hours)	None**
	3		Hold until recovery to $\leq$ grade 1, and then restart at reduced dose.
	4	Discontinue treatment	
Rash	1	No intervention	None
	2	Any of the following: minocycline a , topical tetracycline or clindamycin, topical silver sulfadiazine, diphenhydramine, oral prednisone (short course)	None**
	3		Hold until recovery to $\leq$ grade 2, and then restart the dose.
	4	Discontinue treatment	
Other toxicity	$\geq 2$ prolonged clinically significant toxicity	Treatment as appropriate	Hold until recovery to $\leq$ grade 1, and then restart at reduced dose.

\* If no recovery after 14 days of holding drug, patients should be discontinued from the study

\*\* If dose has been previously held for grade 2 rash or diarrhea, and grade 2 symptoms recur, or if the patient finds the symptoms unacceptable, hold dose until recovery to  $\leq$  grade 1 and then reduce the dose.

a Recommended dose: 200 mg p.o. b.i.d. (loading dose), followed by 100 mg p.o. b.i.d. for 7-10 days.

If symptoms of the same degree reoccur after re-initiating the treatment at reduced dose a further dose reduction will be required or patients should be discontinued from the study.

Dosing may be interrupted for a maximum of 14 days if clinically indicated and if the toxicity is not controlled by optimal supportive medication. Patients who require an interruption in dosing of  $> 14$  days will discontinue treatment and be taken off study.

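### Section 6.1.1 orders interruption and a reduced dose for every drug-related AE, while Table 2 in the same section leaves the dose unchanged for mild rash and diarrhea

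*Combined protocol and SAP*

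**What the plan says.** Section 6.1.1 holds two sets of instructions.

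**The narrative.** "Upon the onset of an AE deemed by the investigator to be related to the study drug, treatment will be interrupted until AE resolution". After that, the drug is to be "then restarted at reduced dose of erlotinib". A further rule follows: "Once a patient has a dose reduction for toxicity, the dose will not be re-escalated except in the case of erlotinib related rash". The preceding paragraph opens by naming diarrhea and rash as the main side effects.

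**Table 2.** It is introduced with "The following guidelines in Table 2 outlines dose adjustments according to the most common toxic effects".
- Grade 1 rash and grade 1 diarrhea: "No intervention", and no dose modification.
- Grade 2 rash and diarrhea: supportive treatment and no dose modification, subject to a footnote. The footnote begins "If dose has been previously held for grade 2 rash or diarrhea, and grade 2 symptoms recur" and adds symptoms that the patient finds unacceptable. Only in those cases is drug held to grade 1 or lower and the dose then reduced.
- Grade 3 rash: hold until the rash is no worse than "grade 2, and then restart the dose".
- Other toxicity: hold and reduce only if it is grade 2 or higher, prolonged and clinically significant.

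The text under Table 1 adds two rules: rash allows re-escalation once it is grade 2 or lower, and more than one toxic effect calls for a reduction. The text closing Table 2 says that patients who need a hold of more than 14 "days will discontinue treatment and be taken off study".

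**Doses and tablets.** Table 1 steps down from 150 to 100 to 50 mg/day. Section 6.1 gives erlotinib once daily. Section 6.3 describes a film-coated 150 mg tablet and names no other strength.

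**The concern.** For a patient with a single grade 1 rash or diarrhea, the two instructions cannot both be followed. The narrative sentence is mandatory in form and covers every related AE. It is not a default for events that the table leaves out: the text around it is about diarrhea and rash, the sentence after it exempts rash only from the ban on re-escalation, and Table 2 has its own row for other toxicity. No sentence says which instruction prevails. The synopsis and Sections 3.1 and 3.1.2 refer to Section 6.1.1 as a whole, which contains both.

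Section 1.1.3 lists rash and diarrhea first among the most frequent AEs with single-agent erlotinib, so the conflict concerns ordinary patients. Sites could dose the same patient differently. That would affect the exposure summaries planned in Section 8.2.2 (duration, dose per day, cumulative dose). It could also affect how long a patient stays on treatment and under scheduled tumor assessment, in a treatment phase of 30 patients at 5 centers (Sections 3.2 and 3.3).

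**Working it through.** The plan states no figure to reproduce. The check is a comparison of text, followed by two small calculations.

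**1. Row-by-row comparison.** The narrative rule is: interrupt until resolution, then restart at a reduced dose.

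| Table 2 rows | Table 2 action | Against the narrative |
|---|---|---|
| Rash 1, rash 2, diarrhea 1, diarrhea 2 (4 rows) | No dose change; the grade 2 rows carry the footnote | Contradicts |
| Rash 3 (1 row) | Hold, then restart; reduction not stated | Unclear restart dose, different recovery grade |
| Diarrhea 3, other toxicity (2 rows) | Hold to grade 1 or lower, then reduce | Same action, different recovery grade |
| Keratitis 2 (1 row) | Hold to recovery, then reduce | Agrees |
| Keratitis 3 or higher, diarrhea 4, rash 4 (3 rows) | Stop treatment | Specific stopping rule |

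Total: 4 + 1 + 2 + 1 + 3 = 11 rows. The outright conflict is the four rows with no dose change. The other-toxicity row adds a conflict of scope: the narrative also catches grade 1 events and short or clinically unimportant grade 2 events, which that row leaves alone.

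**2. Which text is intended.**
- The footnote to the grade 2 rows sets conditions for holding and reducing. If every related grade 2 event were already held and reduced at onset, those conditions would have no purpose.
- Section 7.3.2 treats dose reduction for diarrhea as something needed only in some cases.
- The table lets a patient with grade 3 rash restart while grade 2 rash is still present. A rule that interrupts for any related AE would not allow this.

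All three point to Table 2.

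**3. Dose consequence of following the narrative.** After one reduction: (150 − 100)/150 = 33% lower. After two: (150 − 50)/150 = 67% lower. For diarrhea the reduction is permanent, because the only exception to the ban on re-escalation is rash. For rash it is reversible.

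**4. Off-study consequence.** Under the narrative, a grade 1 rash or diarrhea that has not resolved keeps the patient on hold. Past 14 days, the closing text takes the patient off study. Under Table 2 the same patient, with that single toxicity, stays on 150 mg/day.

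**5. Tablets.** 100/150 = 0.67 of a tablet and 50/150 = 0.33 of a tablet. Whole tablets give multiples of 150 mg and half tablets give multiples of 75 mg. Neither reduced daily dose can be made from whole or half 150 mg tablets, and no splitting instruction is given.

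**The case against.** The best defense is that Section 6.1.1, read as a whole, already limits the sentence. It says that reductions may take place and can follow the worst-affected system, and it requires grading. Table 2 is introduced as the guide for the most common toxicities. The text closing the table allows interruption when clinically indicated and when supportive medication has not controlled the toxicity. A sensible investigator would use the table. This softens the sentence, but it does not remove an order worded as mandatory, and nothing gives the table precedence.

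The defense is right about size, and three stronger readings should be resisted.

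- **A measurable loss of PFS information.** A reader might infer that a predictable number of patients leave the study under the narrative and none under Table 2, with a correspondingly wider confidence interval for the median. The documents give no frequency or duration for mild rash or diarrhea. Table 2's own footnotes can also take a patient with grade 2 symptoms off study. The synopsis collects survival after discontinuation, and Section 8.1.1 counts death as an event, so patients who leave may still contribute events. PFS is only summarized by Kaplan-Meier methods.
- **No rash row agrees with the narrative.** A reader might count grade 4 rash as a further conflict. A specific stopping rule for life-threatening toxicity is a normal exception to a general rule.
- **Reduced doses are impossible to give.** Section 6.3 does not say that 150 mg is the sole strength supplied. The documents support only the statement that no other strength is named.

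**Conclusion.** The narrative sentence is wrong as written. It contradicts four of 11 Table 2 rows outright, is wider than the other-toxicity row, and leaves the restart dose after grade 3 rash unclear. The table is the intended rule.

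For a site that follows the sentence literally, a single mild toxicity costs the patient one third of the daily dose after the hold. Discontinuation follows if the hold passes 14 days. The comparison assumes one toxicity at a time, because the text under Table 1 calls for a reduction when there is more than one. How many patients would be affected, and by how much PFS would shift, cannot be stated from the documents. The correction is worth making for consistent dosing; it does not bear on the sample size or the endpoint definition.

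The tablet gap is secondary and independent. Even under Table 2 alone, grade 2 keratitis and grade 3 diarrhea require a reduced dose, and the plan states no way to supply it.

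**What to change.** 1. Replace the narrative sentence in Section 6.1.1 with: *When Table 2 calls for a hold, treatment will be interrupted until recovery to the grade given in Table 2 and restarted at the dose given in Table 2.*
2. In the grade 3 rash row, state whether treatment restarts at the same or the reduced dose. That choice is the sponsor's.
3. In Section 6.3, list the tablet strengths that deliver 100 and 50 mg/day.

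Do not add a general clause that Table 2 prevails over Section 6.1.1. The table is part of that section, and such a clause would override the rule under Table 1 to reduce the dose for more than one toxic effect. That rule and the rule on re-escalation after rash should stay.

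The cost is three short text edits, plus supply of further tablet strength(s) to 5 centers if this is not already planned.

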### **7.3.2 Diarrhea, Dehydration, Electrolyte Imbalance and Renal Failure**

Diarrhea has occurred in patients on erlotinib, and moderate or severe diarrhea should be treated with loperamide. In some cases, dose reduction may be necessary. In the event of severe or persistent diarrhea, nausea, anorexia, or vomiting associated with dehydration, erlotinib therapy should be interrupted and appropriate measures should be taken to treat the dehydration. There have been rare reports of hypokalaemia and renal failure (including fatalities). Some reports of renal failure were secondary to severe dehydration due to diarrhea, vomiting and/or anorexia while others were confounded by concomitant chemotherapy. In more severe or persistent cases of diarrhea, or cases leading to dehydration, particularly in groups of patients with aggravating risk factors (concomitant medications, symptoms or diseases or other predisposing conditions including advanced age), erlotinib therapy should be interrupted and appropriate measures should be taken to intensively rehydrate the patients intravenously. In addition, renal function and serum electrolytes including potassium should be monitored in patients at risk of dehydration (Core data sheet, 2009).

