### **7.3.3 Hepatitis, Hepatic Failure**

Rare cases of hepatic failure (including fatalities) have been reported during use of erlotinib. Confounding factors have included pre-existing liver disease or concomitant hepatotoxic medications. Therefore, in such patients, periodic liver function testing should be considered. Erlotinib dosing should be interrupted if changes in liver function are severe (Core data sheet, 2009).

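### Section 6.1.1 orders interruption and dose reduction for any related adverse event, while Table 2 leaves the dose unchanged for grade 1 and most grade 2 rash or diarrhoea

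*Combined protocol and SAP*

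**What the plan says.** All the dosing rules at issue stand in section 6.1.1 of the combined protocol and SAP. The synopsis and sections 3.1 and 3.1.2 refer the reader there for dose reduction.

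- **Running text.** The rule that applies when an event begins reads: "AE deemed by the investigator to be related to the study drug, treatment will be interrupted until AE resolution and then restarted at reduced dose". No grade is mentioned. The text adds: "Once a patient has a dose reduction for toxicity, the dose will not be re-escalated except in the case of erlotinib related rash".
- **Table 1.** The first reduction is from 150 to 100 mg/day, the second to 50 mg/day.
- **Text between the tables.** Rash may be re-escalated once it is at grade 2 or lower. A patient with more than one toxic effect is to have the dose reduced, again with no grade given.
- **Table 2**, titled "Guidelines for management of erlotinib-related toxic effects". For diarrhoea and rash the dose modification entry is None at grade 1 and None with a double-asterisk footnote at grade 2. The footnote asks for a hold and then a reduction in these cases: "If dose has been previously held for grade 2 rash or diarrhea, and grade 2 symptoms recur, or if the patient finds the symptoms unacceptable". The row for other toxicity acts only from grade 2, and only if the toxicity is prolonged and clinically significant.
- **Text after Table 2.** "Dosing may be interrupted for a maximum of 14 days if clinically indicated and if the toxicity is not controlled by optimal supportive medication". A patient who needs more than 14 days off drug stops treatment and leaves the study.
- **Section 7.3.2.** "moderate or severe diarrhea should be treated with loperamide. In some cases, dose reduction may be necessary".

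**The concern.** The sentence and the table apply to the same events. The sentence is triggered by relatedness to the drug, and the table by its title covers drug-related effects. For a mild event one calls for interruption and a lower dose, and the other calls for no change.

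The conflict matters because section 6.1.1 itself names diarrhoea and skin rash as the main side effects of erlotinib. PFS, response and safety all come from one arm of 30 patients (section 3.2) at five centres (section 3.3), intended to start at 150 mg/day. Two centres could give different doses after the same event, each with a protocol text in support. The exposure summaries in section 8.2.2 would show the variation afterwards but would not prevent it.

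**Working it through.** The plan states no figure on this point, so the check is a comparison of the two rules, row by row.

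| Related event | Running text of 6.1.1 | Table 2 | Result |
|---|---|---|---|
| Diarrhoea or rash, grade 1 | Interrupt until resolved, restart lower | No change | Conflict |
| Diarrhoea or rash, grade 2, footnote not triggered | Interrupt until resolved, restart lower | Treat symptoms, no change | Conflict |
| Diarrhoea or rash, grade 2, footnote triggered | Interrupt until resolved, restart lower | Hold to grade 1 or lower, then reduce | Same dose, different restart point |
| Diarrhoea, grade 3 | Interrupt until resolved, restart lower | Hold to grade 1 or lower, then reduce | Same dose, different restart point |
| Rash, grade 3 | Interrupt until resolved, restart lower | Hold to grade 2 or lower, then restart; dose level not stated | Different restart point; dose unclear |
| Other toxicity, grade 1, or grade 2 that is brief or not clinically significant | Interrupt until resolved, restart lower | No action called for | Conflict |

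**Which text is out of line?** Two other passages bear on this.

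1. The text after Table 2 makes interruption depend on clinical need and on failure of supportive treatment. An ungraded duty to interrupt does not meet that condition; Table 2 does.
2. Section 7.3.2 gives loperamide for moderate or severe diarrhoea and expects reduction in only some patients. Under the running text every related case would be reduced.

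Both fit Table 2, so the running-text sentence is the one to change.

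**Size for one patient.** From Table 1, the first step is (150 − 100) / 150 = 33.3%. For diarrhoea it cannot be reversed, since only rash may be re-escalated.

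**Effect of the 14-day limit.** The running text keeps the patient off drug until the event resolves. If a grade 1 rash persists beyond 14 days, the limit then ends treatment and takes the patient off study. Table 2 would never have stopped the drug for that rash.

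**The case against.** The strongest reply is that section 6.1.1, read as a whole, settles the matter. It opens by saying that reduction or interruption may take place, adds "Dose reductions can be made according to the system exhibiting the greatest degree of toxicity", has all toxicities graded by CTC-AE, and then gives a graded table. A specific table after a general sentence would normally govern, and a careful clinician would probably read it so. That is a fair account of the likely intent, but it does not remove the conflict. The disputed sentence is mandatory, the table is labelled as guidelines, and no text gives the table precedence.

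A reader might also infer more than the documents support:

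- **That the whole protocol agrees with Table 2.** It does not. Section 7.3.3 says "Erlotinib dosing should be interrupted if changes in liver function are severe", which is a higher bar than the other-toxicity row. The sentence on more than one toxic effect would reduce the dose for coexisting grade 1 rash and diarrhoea, which sits better with an ungraded approach.
- **That the rash re-escalation rule shows the running text to be wrong.** It does not separate the two rules. A rash reduced under the running text has resolved by restart, and one reduced under the footnote is at grade 1 or lower. Either already meets the re-escalation threshold.
- **That Table 2 spares only a first grade 2 episode.** The footnote needs a previous hold for grade 2 followed by recurrence, or symptoms the patient finds unacceptable. A repeat tolerable episode with no earlier hold is also left unchanged.
- **That the fall in the arm's mean dose can be estimated or bounded.** With an assumed share s of patients reduced once, the mean would be 150 − 50s mg/day. The documents give no value for s. The formula is not a bound either: it leaves out days off drug and second reductions, which lower the dose further, and rash re-escalation, which raises it.
- **That an efficacy comparison is biased.** There is one arm, and PFS is summarised by Kaplan-Meier methods (section 8.2). No between-arm contrast exists to bias.

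**Conclusion.** The inconsistency is real and should be fixed. For related grade 1 rash or diarrhoea, and for grade 2 where the footnote is not triggered, the running text of section 6.1.1 and Table 2 give opposite instructions with no order of precedence. The sentence also goes further than the other-toxicity row.

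The documented size is per patient: a 33% dose cut for a mild event, without re-escalation for diarrhoea, and possible removal from the study if a mild event outlasts 14 days. These consequences assume that a site follows the sentence literally; the documents do not show how often that would happen. No arm-level dose effect can be stated, and no sample size, precision or other statistical figure in the plan changes. This is a fault in the dosing instructions and not a statistical error.

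**What to change.** Amend section 6.1.1 as follows.

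1. Replace the disputed sentence with: *For related AEs, dose interruption, restart and reduction follow Table 2 and its footnotes; where Table 2 states None, the dose is unchanged; the event-specific rules in section 7.3 also apply.*
2. Limit the sentence on more than one toxic effect to cases where at least one of the toxicities requires a dose change under Table 2.
3. As clarifications only, have the sponsor state the restart dose after grade 3 rash (same or reduced) and the grade to which grade 2 keratitis must recover. Table 2 gives neither, and no default is proposed here.

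The cost is a wording amendment through the usual approvals in section 12. It needs no additional patients, visits, data or analyses.
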